17.0 DATA MANAGEMENT

17.1 RECORD RETENTION

It is required that a copy of all records (e.g., informed consent documents, source documents, safety reports, study device dispensing record, etc.) which support CRFs for this study, be retained in the files of the responsible Investigator for the latter of the following:

- At least two (2) years after study completion
- At least two (2) years after Sponsor receives approval from the local governing regulatory authority
- For the period required by the local governing authority and reviewing IRB/EC.

Sponsor is to be advised prior to destruction of study records and notified if study records are moved to an off-site location for archiving.

If the Principal Investigator retires, relocates, or for other reasons withdraws from the responsibility of keeping the study records, custody must be transferred to a person who will accept the responsibility. Vascular Dynamics, Inc. must be notified in writing of the name and address of the new custodian.

18.0 PROTOCOL AMENDMENTS

An amendment to the Protocol may be proposed by the Sponsor, or by an Investigator with prior Sponsor approval. The amendment must be submitted to the IRB/EC and its implementation can take place only after IRB/EC approval.

19.0 PROTOCOL DEVIATIONS

The Investigator will not deviate from the Investigational Plan without the prior written approval of Vascular Dynamics, Inc., except in medical emergencies or in unforeseen, isolated instances where minor changes are made that will not increase the subject's risk or affect the validity of the investigation. In medical emergencies, prior approval for Investigational Plan deviations will not be required, but Vascular Dynamics, Inc.'s clinical research personnel must be notified within five (5) days of the incident.

All deviations from the Protocol that occur during the study will be captured and the impact of the Protocol deviations on the validity of the clinical study reports will be discussed in the final clinical study report.

20.0 DEVICE ACCOUNTABILITY

Complete traceability records will be kept of all investigational devices during the study. The MobiusHD system and the applicable accessories will be provided by Vascular Dynamics, Inc. The device number will be documented in subject medical records, CRFs and in the center's logs.

Each Investigator will be responsible for the safe storage with restricted access of the investigational materials in their possession, to prevent use of investigational materials by any persons not participating in the study.

After completion of the study, all unused investigational devices must be returned in their original packaging to Vascular Dynamics, Inc., [name].

All Investigators will be responsible for using the investigational device according to the IFU and Protocol and for maintaining product inventory and records.

21.0 INFORMED CONSENT PROCESS

Informed consent shall be obtained in writing from each study subject or legal guardian and the process shall be documented before any procedure specific to the clinical investigation is applied to the subject.

The subject will be asked to read the Informed Consent Form (ICF) and to sign the form to indicate consent to participate in the study.

The research nature of the study will be explained carefully to the subject. The scope and aims of the research will be described together with known or foreseeable benefits, risks and discomforts that subjects may experience. Appropriate alternative treatments will be discussed so that the subject may determine whether or not he or she wishes to participate in the study. The subject must understand that throughout the study his or her participation remains voluntary and protected by the Declaration of Helsinki. The Investigator is responsible for obtaining written (or witnessed) informed consent from potential subjects prior to study entry. Subjects will be given time to read the ICF consent and ask any questions before being asked to sign the form. The ICF (approved by the Sponsor and the IRB/EC) must be signed and dated by the subject and the Investigator. The Investigator will retain the original signed ICF, give one copy to the subject, and send a second copy to the referring Investigator (if applicable).

Subjects may withdraw their consent to participate in the study at any time without prejudice. The Investigator may withdraw a subject if, in his or her clinical judgment, it is in the best interest of the subject, or if the subject cannot comply with the protocol. Attempts should be made to complete any examinations and the Sponsor must be notified of all withdrawals.

Should a Protocol amendment be made, the subject's consent form may be revised to reflect the changes of the Protocol. It is the responsibility of the Investigator to ensure that an amended ICF is approved or reviewed by the IRB/EC, and that it is signed by all subjects subsequently entered in the study, and those currently in the study, if they are affected by the amendment.

If new information becomes available that could significantly affect a subject's future health and medical care, the information shall be provided to the subject in written form. If relevant, all affected subjects shall be asked to confirm their continuing informed consent in writing.

22.0 PREMATURE STUDY TERMINATION

A subject should be removed from the study whenever considered necessary for his or her welfare or when a subject expresses a desire to withdraw from the study. Non-compliance with the Protocol, the occurrence of a SAE or any medical condition that, in the opinion of the Investigator, warrants discontinuation from the study for the safety of the subject, may necessitate discontinuing a subject. If a subject is discontinued, the reason must be entered on the CRF and signed by the Investigator. In case of any questionable situation, the study monitor or Vascular Dynamics, Inc. personnel should be consulted. When a subject is removed from the study as a result of SAE, a final physical examination must be performed. Subjects removed from the study because of an AE will be followed-up until the adverse event has been resolved.

In the case that the occurrence of AEs is greater than anticipated, the clinical investigation will be suspended; in such a case, a safety committee will be arranged to decide if the study

could be continued. The IRB/EC will be notified and the results of the safety committee discussions will be brought to the IRB/EC for review and decision.

Vascular Dynamics, Inc. reserves the right to discontinue any study at any time for administrative reasons including, but not limited to, a decision to discontinue further clinical investigation of the device, improper conduct of the study by the Investigator, and inability to obtain the number of subjects required by the Protocol. Reimbursements for reasonable expenses will be made if such an action is necessary.

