1.0 PROTOCOL SYNOPSIS

TITLE	CALM-FIM_US - C ontrolling and L owering Blood Pressure with the M obiusHD™ - A Prospective Multicenter Safety Study
STUDY OBJECTIVE	To evaluate the safety and performance of the MobiusHD system in subjects with resistant hypertension.
STUDY DESIGN	
This is an open-label, multicenter, first-in-man clinical trial to be conducted inside the United States. Eligible subjects with stage 2 resistant systemic arterial hypertension currently being treated with a minimum of three (3) anti-hypertensive drugs, who consent to study participation will be assigned to treatment with the MobiusHD system.
 
Potential study participants will be consented and then screened at two (2) baseline visits beginning at least 30 days prior to MobiusHD placement. Qualified patients will undergo placement of the MobiusHD under angiographic visualization, and will then be followed for 36 months.
 
Subjects will be enrolled in two (2) phases, as follows:
 
 ▪ Ten subjects will be implanted unilaterally and followed for seven (7) days. ▪ Based on consensus following 7-day clinical outcome analysis by an independent data safety monitoring board (DSMB), 10 additional subjects will be enrolled and implanted bilaterally.
PATIENT POPULATION	Subjects with resistant hypertension receiving at least three (3) anti-hypertensive medications including a diuretic and with no evidence of extracranial carotid disease or significant great vessel/aortic arch atherosclerotic disease.
NUMBER OF PATIENTS	Twenty subjects are to be enrolled at two (2) to ten (10) U.S. clinical sites.
PRIMARY OUTCOME	Safety: Incidence of serious adverse events (SAEs) and unanticipated adverse device effects (UADE) reported for the study population from implantation through six (6) months of follow-up.
SECONDARY OUTCOME	Performance: Decrease in office cuff blood pressure (BP).
ADDITIONAL OUTCOMES	
Change in heart rate
 
Reduction of medication post 6-month follow-up
 
365-Day safety and efficacy
 
Long term safety and efficacy – one (1) to three (3) years

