9.0 STUDY COMPLETION

After the subject has completed the 3-Year follow-up visit, a Subject Termination iCRF must be completed. During the course of the study, it is possible that subjects will be withdrawn from the study early. Factors leading to subject withdrawal may include, but are not limited to, the following:

- **Subject Withdrawal** - A subject may voluntarily withdraw from the study at any time without affecting his or her future medical treatment or benefits. In addition, the Investigator may withdraw a subject from the study if the subject refuses further testing or follow-up evaluations, or for any other reason as determined by the Investigator.
- **Subject Lost to Follow-Up** – If the Investigator has attempted to contact a subject at least three (3) times and receives no response, the subject may be lost to follow-up. The research staff should document at minimum three (3) attempts to contact the subject prior to terminating the subject from the trial.
- **Subject Death** - When a subject expires, the Serious Adverse Event and Subject Termination iCRFs must be completed promptly. Source documents such as death summary, autopsy report (if done), and a copy of the death certificate should be redacted of personal identifiers and provided to the designated clinical monitor and DSMB to describe the cause of the subject's death. The Investigator will notify the IRB/EC and Sponsor within 24 hours of learning of the event.

The Termination iCRF should be completed for each study subject, to record date and reason for early termination (if subject does not complete the study) or at the final visit (if subject completes all study time points).

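### Sections 9 and 22 do not separate stopping study procedures from leaving safety follow-up, so an implanted subject removed before 6 months can have unobserved events in the primary safety window

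*Combined protocol and SAP*

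**What the plan says.** The synopsis (Section 1.0) defines the primary outcome as the incidence of SAEs and UADEs "reported for the study population from implantation through six (6) months of follow-up". Safety at 365 days and from one to three years is listed among the additional outcomes.

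The exit rules are in two places:

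- Section 22.0 names as possible grounds for discontinuation "Non-compliance with the Protocol, the occurrence of a SAE or any medical condition that, in the opinion of the Investigator", warrants it for the subject's safety. The wording is permissive, and doubtful cases are to be discussed with the monitor or the sponsor.
- Section 9.0 lets the investigator withdraw a subject "if the subject refuses further testing or follow-up evaluations, or for any other reason as determined by the Investigator".

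For what happens after removal, Section 22.0 has two sentences. For an SAE: "When a subject is removed from the study as a result of SAE, a final physical examination must be performed". For an AE generally: "Subjects removed from the study because of an AE will be followed-up until the adverse event has been resolved". Neither sentence refers to the 6-month window, and neither covers removal for non-compliance or at the investigator's discretion.

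Section 3.3 says that the catheter is withdrawn and the implant left in the carotid sinus. Section 13.0 plans descriptive summaries only: AEs as the number and percentage of patients affected, plus an individual profile and narrative for each subject. It gives no rule for incomplete follow-up and names no denominator.

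**The concern.** With a permanent implant, leaving the study does not end exposure. The protocol nevertheless treats discontinuation as a single step that ends both study procedures and the search for new safety events. Under its own rule, an implanted subject removed for an AE that resolves on Day 3 need not be contacted after Day 3. Section 11.3 anticipates events that can arise well after that, among them device fracture or dislocation, blood pressure disturbance beyond 30 days, stroke and death.

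The internal contrast is telling. Section 7.0 gives a subject in whom no implant could be placed a minimum follow-up to the 30-Day visit, longer if an AE is ongoing. A subject who carries the implant and is removed for an AE has no stated minimum.

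Safety is the sole primary outcome, the trial is first-in-man, and at most 20 subjects are planned. One subject is 1/20 = 5 percentage points overall and 1/10 = 10 points within a cohort, so a few unobserved outcomes change how the result reads.

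**Working it through.** **1. Does any other text restore follow-up to 6 months?**

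- Section 11.0 runs AE reporting from initial treatment to the Month 36 visit, but a removed subject has no further visits.
- Section 11.2 has all exposed subjects evaluated for AEs and each AE followed until it resolves or the subject is stable. That follows known events; it schedules no contact to find new ones after removal.
- Section 21.0 asks for attempts to complete examinations at withdrawal and for notice to the sponsor. It does not require contact to 6 months.
- Section 9.0 records the date and reason of termination only.

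None of these closes the gap.

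**2. What is lost, by reason and time of removal**

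| Removal | Follow-up stated | Effect on the outcome |
|---|---|---|
| SAE, before 6 months | Final physical examination; follow-up until the event resolves | Subject already counts as having an SAE; later SAEs, event types, UADEs and death are lost |
| Non-serious AE, before 6 months | Until that AE resolves | Can be counted as SAE-free without having been observed |
| Non-compliance or discretion, before 6 months | None beyond the Section 21.0 attempts | Can be counted as SAE-free without having been observed |
| Any reason, after 6 months | As above | Primary window unaffected; 1- to 3-year safety data lost |

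**3. Size**

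Section 8.2 gives the sample size of up to 20 without an event rate, precision or power, so there is no planned figure to reproduce. The removal rate is not in the documents. *Assumption:* m = 1, 2 or 3 of 20 are removed before 6 months without an observed SAE.

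Exact (Clopper-Pearson) two-sided 95% upper limit U for x events in n subjects:

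- x = 0: U = 1 − 0.025^(1/n). For n = 20, U = 16.8%; for n = 10, U = 30.8%.
- x > 0: U solves Σ_{k=0..x} C(n,k) U^k (1−U)^(n−k) = 0.025.

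Worst case: each of the m removed subjects has a later uncaptured SAE, so the true count is m/n while 0/n is reported.

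| m | Reported 0/20, U | Completers only 0/(20−m), U | Worst case m/20, U |
|---|---|---|---|
| 1 | 0%, 16.8% | 0/19, 17.6% | 5%, 24.9% |
| 2 | 0%, 16.8% | 0/18, 18.5% | 10%, 31.7% |
| 3 | 0%, 16.8% | 0/17, 19.5% | 15%, 37.9% |

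Within one cohort of 10, a reported 0/10 (U = 30.8%) becomes 10%, 20% or 30% in the worst case, with U = 44.5%, 55.6% or 65.2%.

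Dropping removed subjects from the denominator barely moves the limit (16.8% to at most 19.5%), so a completers-only analysis would not reveal the problem. Only observation of the removed subjects, or an explicit worst-case calculation, does.

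**The case against.** The strongest reply is that the planned AE summary is by patient. A subject removed for an SAE is already in the numerator, and ending follow-up cannot lower the percentage of patients with any SAE. That stands. A reader might infer that removal for an SAE deflates the primary rate; on a patient-level count it does not. The loss there is in repeat events, event types, UADEs and deaths. Undercounting of patients is confined to removals without an observed SAE.

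Other limits also stand:

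- The rule of follow-up until resolution covers AE removals only. It should not be read as applying to non-compliance, where the text is silent and the gap is wider.
- A reader might infer that the plan excludes removed subjects from the denominator. No section says so: the synopsis refers to the study population, and Section 13.0 is silent.
- Lost person-time is a tempting measure. Three removals each losing 150 of 180 days would be 450 of 20 × 180 = 3,600 person-days, or 12.5%. But the plan reports nothing per person-day, and that figure rests on one assumed scenario.
- That removed subjects are at higher risk, or that the blood pressure summary would be left with those who tolerated the device, is plausible but has no support in figures from the documents.
- Discontinuation is permissive and hedged by the investigator's judgement. With 20 individual narratives, an early exit would be visible to a careful reader.

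This last point softens the concern without answering it. A narrative shows that observation stopped, not what happened afterwards. The absence of hypothesis testing does not help either, because a descriptive safety rate still needs the events to be ascertained.

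**Conclusion.** The concern holds as a defect in the stated follow-up rule. Sections 9.0 and 22.0 let safety observation of an implanted subject end before 6 months, and no other section restores it. The consequence depends on why and when the subject leaves. Patient-level undercounting of SAEs is possible for removals before 6 months due to non-compliance, a non-serious AE or investigator discretion. For SAE removals the loss is of subsequent events. For removals after 6 months it is confined to the longer-term outcomes.

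With 1 to 3 such removals among 20, a reported rate of 0% could conceal a true rate of 5% to 15%, and the exact upper limit would move from 16.8% to between 24.9% and 37.9%. These figures rest on two assumptions, the number removed and that every one has an uncaptured event. They mark the worst case and are not a forecast. The textual gap is certain; its size in practice cannot be derived from the documents. It should be corrected, since safety is the primary outcome and the remedy is small.

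**What to change.** 1. In Sections 9.0 and 22.0, distinguish stopping study procedures from leaving safety follow-up. State that an implanted subject who stops procedures for any reason other than withdrawing consent to data collection stays in SAE/UADE and vital-status follow-up, by visit or telephone, through 6 months and on to 36 months. The investigator's freedom to stop study procedures is unchanged.
2. In Section 13.0, name all implanted subjects as the denominator for the primary outcome.
3. In Section 13.0, report the number of implanted subjects with incomplete 6-month follow-up, by reason, overall and by cohort. Add a worst-case sensitivity analysis in which each such subject without an observed SAE or UADE is counted as having one.

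The cost is revised protocol and consent wording, a data-collection form for contacts after discontinuation, and some additional contacts. No new procedure or subject is needed.

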23.0 REGULATORY AND HEALTH AUTHORITY AUDITS

The U.S. Food and Drug Administration (FDA), European authorities, and the local state health authorities may request access to all study records, including source documents, for inspection. The Investigator and hospital staff are requested to cooperate with these audits. The Investigator must notify the Sponsor of any health authority audit as soon as notification of such audit is made. A representative or designee of the Sponsor may also conduct similar audits and may be present during health authority audit.

24.0 SUBJECT PRIVACY AND CONFIDENTIALITY

The subject's name and personal data will remain confidential and will not be published in any way. However, the Sponsor's monitor or representative and regulatory representatives, auditors and inspectors may have access to medical files in order to verify authenticity of data collected.

APPENDIX I: IMAGING GUIDELINES

APPENDIX II: SAMPLE INFORMED CONSENT

APPENDIX III: SAMPLE CASE REPORT FORMS

APPENDIX IV: BP MEASUREMENT INSTRUCTIONS

APPENDIX V: CAROTID SINUS MASSAGE INSTRUCTIONS

APPENDIX VI: INSTRUCTIONS FOR USE

APPENDIX VII: GUIDELINES FOR THE SIX-MINUTE WALK TEST
